## 10.5. APPENDIX 5: Protocol Amendment History

### Amendment 1, 22 Oct 2021: Current Amendment

This amendment is considered to be substantial based on the criteria set forth in Article 10(a) of Directive 2001/20/EC of the European Parliament and the Council of the European Union.

#### Main Rationale for the Amendment

1. To change the dose levels of mRNA-1283 to CCI [REDACTED] and of mRNA-1283.211 to CCI [REDACTED], and to remove the mRNA-1283.351 arm. In order to accomplish this, an additional arm of mRNA-1283 was added. The dose modification and removal of mRNA-1283.351 arm was in response to a review of topline results from the interim analysis of the Phase 1 Study mRNA-1283-P101.
2. The study was changed to Phase 2a to reflect that the study is continuing dose-ranging for mRNA-1283 to identify the appropriate dose levels for continued clinical development.
3. The size of each of the arms of the study were increased from 35 to 70 participants to improve the precision in the descriptive summary statistics.
4. Minor changes have been made throughout the protocol to provide additional clarity and correct grammatical or spelling errors.

#### Summary of Major Changes from Original Protocol to Protocol Amendment 1:

Section # and Name	Description of Change	Brief Rationale
Title Page, Signature Page, Protocol Amendment Summary of Changes, and Header	

• Updated the protocol version and date.

• Added Protocol Amendment Summary of Changes for Amendment 1.

	Updated to reflect the new version and date.
Throughout the protocol	

• Minor updates to language

	Updates for improved clarity and to correct grammatical or spelling mistakes.
Title Page, Signature Page, Declaration of Investigator, Protocol Synopsis	

• Changed the protocol title to remove the mention of specific variants of mRNA-1283

	To avoid future changes in the protocol title if additional variants are added to the study.
Title Page, Signature Page, Declaration of Investigator, Protocol Synopsis, Section 1.1 (Study Rationale), Section 3.1 (General Design)	

• Changed study phase to Phase 2a

	Updated to reflect the new dose-ranging nature of the study.

Section # and Name	Description of Change	Brief Rationale
Protocol Synopsis, Section 3.1 (General Design), Section 5.3.1 (Study Vaccine Preparation)	

Changed the dose levels of the mRNA-1283 arms of the study to CCI [REDACTED] (added an arm to the mRNA-1283 portion of the study).

Changed the dose levels of the mRNA-1283.211 arms to CCI [REDACTED].

	Analysis of topline results from the interim analysis of Study mRNA-1283-P101 support a lower dose profile for mRNA-1283. The mRNA-1283-P101 results are currently blinded and interim analysis results of the study will be summarized after study unblinding.
Title Page, Signature Page, Declaration of Investigator, Protocol Synopsis, Section 1.1 (Study Rationale), Section 1.2.3 (mRNA-1283.351), Section 1.2.4 (now Section 1.2.3 Nonclinical Studies), Section 3.1 (General Design), Section 3.3 (Justification for Dose, Control Product, and Choice of Study Population), Section 4 (Study Population), Section 5.1 (Investigational Products Administered), Section 5.3.1 (Study Vaccine Preparation), Section 5.3.4 (Study Vaccine Packaging and Labeling), Section 5.3.5 (Study Vaccine Storage), Section 8.3 (Sample Size Determination), Section 8.5.4.1 (Analysis for the Primary Immunogenicity Objective), Section 10.1 (Appendix 1: Schedule of Events)	1. Removed the mRNA-1283.351 arm of the study	The multivalent vaccine mRNA-1283.211 contains the B.1.351 variant mRNA and so mRNA-1283.351 will not be evaluated separately.
Protocol Synopsis, Section 3.1 (General Design), Section 4 (Study Population), Section 8.3 (Sample Size Determination)	2. Changed the number of participants per arm from 35 to 70	To improve the descriptive summary value of each of the arms of the study.

Section # and Name	Description of Change	Brief Rationale
Protocol Synopsis	3. Changed projected date of first participant enrolled 4. Changed projected date of first participant completed	To reflect updated projected study timelines.
Protocol Synopsis	5. Increased number of planned sites to 13	To reflect the planned increase in the number of sites in the study.
Protocol Synopsis, Section 2 (Objectives and Endpoints)	6. Updated language for the Objectives and Endpoints	To improve clarity in the language surrounding the mRNA-1283 booster vaccines.
Protocol Synopsis, Section 4.2 (Exclusion Criteria)	7. Updated Exclusion Criteria	To improve clarity and align protocol language with other booster study protocols.
Protocol Synopsis, Section 8.6.1 (Primary Analysis)	8. Added statement that the protocol may be amended based on the results of the primary analysis.	Clarifying statement.
Section 1.2.5 (now 1.2.4 Clinical Studies)	9. Removed language stating that no clinical studies with mRNA-1283 have been completed	Study mRNA-1283-P101 has completed enrollment and topline results have been prepared.
Section 1.3.2 (Risks from Study Participation and Their Mitigation)	10. Removed discussion of the potential for vaccine associated enhanced disease	Based on the mRNA-1273-P301 results, there are no data suggestive of vaccine associated enhanced disease.

## List of Abbreviations

Abbreviation	Definition
AE	adverse event
AESI	adverse event of special interest
ANCOVA	analysis of covariance
AR	adverse reaction
bAb	binding antibody
BMI	body mass index
CDC	US Centers for Disease Control and Prevention
CEAC	Cardiac Event Adjudication Committee
CI	confidence interval
COVID-19	coronavirus disease 2019
CRO	contract research organization
CSP	clinical study protocol
CSR	clinical study report
DHHS	Department of Health and Human Services
DSMB	Data Safety Monitoring Board
eCRF	electronic case report form
eDiary	electronic diary
EoS	end of study
FAS	Full Analysis Set
FSH	follicle-stimulating hormone
GLSM	geometric least square mean
GM	geometric mean
GMFR	geometric mean fold rise
GMR	geometric mean ratio
GMT	geometric mean titer
ICF	Informed consent form
IP	investigational product
IRT	interactive response technology
LLOQ	lower limit of quantification
MAAE	medically attended adverse event
MedDRA	Medical Dictionary for Regulatory Activities
mRNA	messenger ribonucleic acid
nAb	neutralizing antibody
NP	nasopharyngeal

Abbreviation	Definition
NTD	N-terminal domain
PI	Principal Investigator
PP	Per-Protocol
PPIS	Per-Protocol Immunogenicity Set
PPIS-Neg	Per-Protocol Immunogenicity Subset-Pre-booster SARS-CoV-2 Negative
PT	preferred term
RBD	receptor-binding domain
RT-PCR	reverse transcriptase polymerase chain reaction
S	Spike
SAE	serious adverse event
SAP	statistical analysis plan
SAR	solicited adverse reaction
SARS-CoV-2	severe acute respiratory syndrome coronavirus 2
SAS	Statistical Analysis System
SD	standard deviation
SOC	system organ class
SoE	schedule of events
SRR	seroresponse rate
TEAE	treatment-emergent adverse event
ULOQ	upper limit of quantification
WHO	World Health Organization
WHODD	World Health Organization drug dictionary

## 1. Introduction

This statistical analysis plan (SAP), which describes the planned analyses for study mRNA-1283-P201, is based on the most recently approved clinical study protocol (CSP) amendment, dated 31-Jan-2022 and the most recent electronic case report form (eCRF) Version v2.003, dated 18-Feb-2022.

### Summary of Major Changes in SAP, Version 2.0

Section	Brief Description of Changes	Rationale
3.1.1/2	Inclusion of binding antibody variant B1.1.529 to endpoints.	Analysis requirement
3.2.1	Remove the comparison of immune response between Part B treatment arms and Part A mRNA-1273 CCI.	Consistency with protocol
6.4.2	Inclusion of analysis at Day 91. Remove mRNA-1273 CCI from Part B analysis (ANCOVA model). Remove stratified Miettinen-Numinen analysis.	Analysis requirement and consistency with protocol

In addition to the information presented in the statistical analysis plan section of the protocol (Section 8) which provides the main analyses for this study, this SAP provides statistical analysis details/data derivations. It also documents modifications or additions to the analysis plan that are not “principal” in nature and result from information that was not available at the time of protocol finalization.

Study mRNA-1283-P201 is a Phase 2a, randomized, stratified, observer-blind study to evaluate the immunogenicity and safety of mRNA-1283 vaccine boosters for severe acute respiratory syndrome coronavirus 2 (SARS-CoV2).

The PPD Biostatistics and programming team, designee of Moderna Biostatistics and Programming department, will perform the statistical analysis of the safety, reactogenicity, and immunogenicity data; Statistical Analysis System (SAS) Version 9.4 or higher will be used to generate all statistical outputs (tables, figures, listings, and datasets). The SAP will be finalized and approved prior to the primary analysis clinical database lock and treatment

unblinding for the study. If the methods in this SAP differ from the methods described in the protocol, the SAP will prevail.

## **2. Study Objectives**

### **2.1. Part A Objectives**

#### **2.1.1. Primary Objectives**

The primary objective is to assess the safety, reactogenicity and immunogenicity of the mRNA-1283 and mRNA-1283.211 vaccines as single booster doses for participants 18 years and older who were previously vaccinated with mRNA-1273 primary series.

#### **2.1.2. Secondary Objectives**

The secondary objective is to evaluate the immunogenicity of the mRNA-1283 and mRNA-1283.211 vaccines as single booster doses at all immunogenicity time points (Days 1, 15, 29, 91, 181 and 366).

#### **2.1.3. Exploratory Objectives**

The exploratory objectives are the following:

- To characterize cellular immunogenicity
- To conduct active detection of symptomatic and asymptomatic SARS-CoV-2 infection
- To assess the genetic and/or phenotypic relationships of isolated SARS-CoV-2 strains to the vaccine sequence

## **2.2. Part B Objectives**

### **2.2.1. Primary Objectives**

The primary objective is to assess the safety, reactogenicity and immunogenicity of the mRNA-1283.529 vaccine administered as the second booster dose to participants 18 years and older who were previously vaccinated with mRNA-1273 primary series and a mRNA-1273 booster dose.

#### **2.2.2. Secondary Objectives**

The secondary objective is to assess the immunogenicity of the mRNA-1283.529 vaccine at all immunogenicity time points (Days 1, 15, 29, 91, 181 and 366).

### **2.2.3. Exploratory Objectives**

The exploratory objectives are the following:

- To characterize cellular immunogenicity
- To conduct active detection of symptomatic and asymptomatic SARS-CoV-2 infection
- To evaluate the genetic and/or phenotypic relationships of isolated SARS-CoV-2 strains to the vaccine sequence

## **3. Study Endpoints**

### **3.1. Part A Endpoints**

#### **3.1.1. Primary Endpoints**

The primary objective will be evaluated by the following endpoints:

- Frequency and grade of each solicited local and systemic reactogenicity adverse reaction (AR) during a 7-day follow-up period after vaccination
- Frequency and severity of any unsolicited adverse events (AEs) during the 28-day follow-up period after vaccination
- Frequency of any serious AEs (SAEs), medically attended AEs (MAAEs), AEs leading to withdrawal from study participation, and AEs of special interest (AESIs) from Day 1 to end of study (EoS)
- Immune response of the mRNA-1283 and mRNA-1283.211- vaccines against the ancestral SARS-CoV-2 and SARS-CoV-2 variants, including B.1.351 and B.1.1.529, at Day 29 by geometric mean titer (GMT), geometric mean fold rise (GMFR), and seroresponse rate (SRR)
- To compare descriptively the immune response elicited by the mRNA-1283 and mRNA-1283.211 - vaccines with that elicited by the mRNA-1273 vaccine when administered as a booster, at Day 29 by GMT, GMFR, and SRR

#### **3.1.2. Secondary Endpoints**

The secondary objective will be evaluated by the following endpoints:

Immune response of the mRNA-1283 and mRNA-1283.211 vaccines against the ancestral SARS-CoV-2 and SARS-CoV-2 variants, including B.1.351 and B.1.1.529, at all immunogenicity time points (Days 1, 15, 29, 91, 181 and 366) by GMT, GMFR, and SRR.

### **3.1.3. Exploratory Endpoints**

The exploratory objective will be evaluated by the following endpoints:

- Frequency, magnitude, and phenotype of antigen specific B- and T-cells, to include B-cell and T-cell receptor repertoires
- Laboratory-confirmed asymptomatic or symptomatic SARS-CoV-2 infection will be defined in participants:
  - Negative SARS-CoV-2 anti-nucleocapsid antibody blood test at Day 1 that becomes positive at Day 29 or later, OR
  - Positive SARS-CoV-2 reverse transcriptase polymerase chain reaction (RT-PCR) from nasopharyngeal swab
- Comparison of the SARS-CoV-2 genetic sequence of viral isolates with the vaccine sequence and characterization of immune responses to vaccine breakthrough isolates

## **3.2. Part B Endpoints**

### **3.2.1. Primary Endpoints**

The primary objective will be evaluated by the following endpoints:

- Frequency and grade of each solicited local and systemic reactogenicity AR during a 7-day follow-up period after vaccination
- Frequency and severity of any unsolicited AEs during the 28-day follow-up period after vaccination
- Frequency of any SAEs, MAAEs, AEs leading to withdrawal from study participation, and AESIs from Day 1 to EoS
- Immune response of the mRNA-1283.529 vaccine by dose level against SARS-CoV-2 Omicron variant (B1.1.529) at Day 29 by GMT, GMFR, and SRR

### **3.2.2. Secondary Endpoints**

The secondary objective will be evaluated by the following endpoints:

Immune response of the mRNA-1283.529 vaccine by dose level against the ancestral SARS-CoV-2 and SARS-CoV-2 variants, including B.1.529, at all immunogenicity time points (Days 1, 15, 29, 91, 181 and 366) by GMT, GMFR, and SRR.

### 3.2.3. Exploratory Endpoints

The exploratory objective will be evaluated by the following endpoints:

- Frequency, magnitude, and phenotype of antigen-specific B- and T-cells, to include B-cell and T-cell receptor repertoires
- Laboratory-confirmed asymptomatic or symptomatic SARS-CoV-2 infection will be defined in participants:
  - Negative SARS-CoV-2 anti-nucleocapsid antibody blood test at Day 1 that becomes positive at Day 29 or later, OR
  - Positive SARS-CoV-2 RT-PCR from nasopharyngeal swab
- Comparison of the SARS-CoV-2 genetic sequence of viral isolates with the vaccine sequence and characterization of immune responses to vaccine breakthrough isolates

## 4. Study Design

### 4.1. Overall Study Design

This is a Phase 2a study that consists of two parts: Part A is an observer-blind, stratified, randomized design to evaluate the immunogenicity, safety, and reactogenicity of mRNA-1283 and mRNA-1283.211 vaccines administered as a single booster dose to participants 18 years and older who were previously vaccinated with mRNA-1273, respectively. Part B is an open-label design to evaluate the immunogenicity, safety, and reactogenicity of mRNA-1283.529 administered as the second booster dose to participants 18 years and older who were previously vaccinated with mRNA-1273 primary series and a single mRNA-1273 booster dose (i.e., three doses of mRNA-1273).

Up to 420 participants in Part A who received the primary series of mRNA-1273 CCI with appropriate documentation at least 6 months prior will be randomized 1:1:1:1:1 (i.e., up to 70 participants per treatment group) to receive a single boost of mRNA-1283 at one of three dose levels CCI, a single boost of mRNA-1283.211 at one of two dose levels CCI, or a single dose of the active comparator, mRNA-1273 at a single dose level CCI (Table 1-1).

Up to 140 participants in Part B who received the primary series of mRNA-1273 CCI and a first booster dose of mRNA-1273 CCI at least 3 months prior will be enrolled in a 1:1 ratio (i.e., up to 70 participants per dose level) to receive a single boost of mRNA-1283.529 as the second booster dose at one of two dose levels CCI (Table 1-2).

Enrollment in both parts of this study will be stratified by age with two age strata: 18-55 years of age and  $\geq$ 56 years of age, with at least 20% but no more than 50% of participants 56 years of age or older. Those with documented prior SARS-CoV-2 infection are eligible to participate if also previously vaccinated with mRNA-1273. Prior infection status will be confirmed by anti-nucleocapsid antibody testing of all participants.

**Table 1-1: Part A Treatment Groups:**

Treatment Group	Vaccine	Dose Level 	N
1	mRNA-1283	CCI	70
2			70
3			70
4	mRNA-1283.211		70
5			70
6	mRNA-1273		70

 Dose levels for mRNA-1283.211 and mRNA-1273 are total mRNA in 1:1 ratio of mRNA-1283 and mRNA-1283.351 or mRNA-1273 and mRNA-1283.351, respectively.

**Table 1-2: Part B Treatment Groups:**

Treatment Group	Vaccine	Dose Level 	N
1	mRNA-1283.529	CCI	70
2		CCI	70

Participants in both parts will have up to 7 study visits; 6 visits if screening and randomization/enrollment are performed on the same day. Study vaccine will be administered as a single dose on Day 1. Additional safety and immunogenicity study visits will occur on Days 8 (safety call only), 15, 29, 91, 181, and 366 (end of study [EoS]). Study visits will include scheduled safety phone calls every 2 weeks to collect MAAEs, AESIs, AEs leading to withdrawal, SAEs, and information about concomitant medications associated with these events, as well as to collect information about receipt of non-study vaccinations temporally associated with these events.

At the vaccination visit (Day 1), participants will be instructed how to document and report solicited ARs in a provided electronic diary. Solicited ARs will be assessed for 7 days after the injection (the day of injection and the following 6 days), and unsolicited AEs will be assessed for 28 days after each injection. Medically attended AEs, SAEs, AESIs, and AEs leading to withdrawal will be assessed throughout the study. All participants will be tested for the presence of SARS-CoV-2 anti-nucleocapsid antibodies at Days 1, 29, 91, 181, and 366, as well as by nasopharyngeal swab RT-PCR on Days 1, 29, 91, 181, and 366. Active surveillance for intercurrent or breakthrough SARS-CoV-2 infection will occur throughout the study and be reported as AEs (confirmed symptomatic infections will be reported as MAAEs if not an SAE). Symptomatic infection will be prompted by signs and symptoms meeting the US Centers for Disease Control and Prevention (CDC) case definition and the case definition from the Phase 3 study (mRNA-1273-P301) for coronavirus disease 2019 (COVID-19), as well as the clinical suspicion of the site investigator. Participants will be asked to contact the study site to arrange for a prompt, thorough, and careful assessment. Participants will have blood sampled at scheduled study site visits (Days 1, 15, 29, 91, 181, and 366) during the study for immunogenicity assessments or other medical concerns according to the investigator's judgment.

#### **4.2. Sample Size and Power**

The sample size for this trial is not driven by statistical assumptions for formal hypothesis testing. The number of proposed participants is considered sufficient to provide a descriptive summary of the safety and immunogenicity of each treatment group. In Part A, up to 420 participants will be randomized to 6 treatment arms in a 1:1:1:1:1:1 ratio to mRNA-1283 at three dose levels, mRNA-1283.211 at two dose levels, and mRNA-1273 at a single dose level, respectively (i.e., up to 70 participants for each treatment group). In Part B, up to 140 participants will be enrolled in two treatment arms of mRNA-1283.529 in a 1:1 ratio.

Enrollment in both parts of this study will be stratified by age with two age strata: 18-55 years of age and  $\geq$ 56 years of age, with at least 20% but not more than 50% of participants 56 years of age or older.

#### **4.3. Randomization**

Randomization will be performed using an interactive response technology (IRT). Participants in Part A will be randomized in parallel according to a 1:1:1:1:1:1 ratio (Arm 1: Arm 2: Arm 3: Arm 4: Arm 5: Arm 6). Participants in Part B will be enrolled in the two

arms sequentially. Enrollment in both parts of this study will be stratified by age with two age strata: 18-55 years of age and  $\geq 56$  years of age, with at least 20% but not more than 50% of participants 56 years of age or older.

#### **4.4. Blinding and Unblinding**

All participants, study staff involved in participant assessment, and Sponsor personnel (or its designees) will be blinded to vaccination assignment until the EoS for Part A.

Preparation of IP for administration will be conducted on site by an unblinded staff member who has no role in the observation or assessment of study participants. A limited number of Sponsor and/or contract research organization (CRO) personnel will be unblinded to perform Data Safety Monitoring Board (DSMB) safety data reviews. Additional information regarding unblinding for Part A is provided in protocol Section 5.3.8. Part B of the study is open-label and therefore unblinded.

At the time of primary analysis (Day 29 for Part A), only pre-identified sponsor and unblinded CRO team members as specified in the study Data Blinding Plan will become unblinded to review treatment level results and individual listings, please also refer to [Section 6.7.](#)

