### **5.3.8. Unblinding (Part A)**

Part A of this study is an observer-blind study. The investigator, study staff, study participants, site monitors, and Sponsor personnel (or its designees) will be blinded to the IP administered until the EoS for Part A, with the following exceptions:

- Unblinded personnel (of limited number) will be assigned to vaccine accountability procedures and will prepare IP for all participants. These personnel will have no study functions other than study vaccine management, documentation, accountability, preparation, and administration. They will not be involved in participant evaluations and will not reveal the identity of IP to either the participant or the blinded study site personnel involved in the conduct of the study unless this information is necessary in the case of an emergency.
- Unblinded medically qualified study site personnel will administer the IP. They will not be involved in assessments of any study endpoints.
- Unblinded site monitors, not involved in other aspects of monitoring, will be assigned as the IP accountability monitors. They will have responsibilities to ensure that sites are following all proper IP accountability, preparation, and administration procedures.
- The DSMB will review unblinded statistical outputs for ad hoc safety reviews triggered by pause rules, should this occur. See [Section 10.2.11](#) for additional information on DSMB and safety review.
- The pre-identified Sponsor team members will become unblinded to treatment group after primary analysis, but not to individual study participant receipt of study vaccine.

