### **8.1. Blinding and Responsibility for Analyses**

Blinding during the study will be conducted as described in [Section 5.2](#). The Sponsor Biostatistics Department or designee will generate the randomized allocation schedule(s) for study treatment assignment. Randomization will be implemented via an IRT.

Participant-level unblinding at the time of the primary analysis will be restricted to an independent unblinded statistician and, as needed, a statistical programmer who will perform the primary analysis, who will have no other responsibilities associated with the study.

The planned study analyses are described in [Section 8.6](#).

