#### **6.7. Primary Analysis**

The primary analysis of safety and immunogenicity will be conducted after Part A participants have completed their Day 29 visit assessments. All data relevant to the primary analysis through Day 29 will be cleaned (as clean as possible) and locked. The primary analysis will be performed by a separate team of unblinded programmers and statisticians. The analysis, including any case of COVID-19, will be presented by treatment group. With the exception of appropriately delegated unblinded study staff, vaccine administrators, and monitors, all personnel involved in the conduct of the trial will remain blinded to individual treatment assignment until unblinding. Investigators will be blinded until after the final database lock for final analysis.

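### SAP 4.4 gives pre-identified sponsor members individual listings at the Part A Day 29 analysis, which protocol 5.3.8 and 8.1 withhold from them; this weakens the sponsor-side blind for the rest of follow-up, and SAP 7 does not declare it

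*SAP*

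**What the plan says.** The documents give different rules for the same analysis.

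- **Protocol 5.3.8**, in its list of exceptions to the Part A blind: "The pre-identified Sponsor team members will become unblinded to treatment group after primary analysis, but not to individual study participant receipt of study vaccine".
- **Protocol 8.1**: "Participant-level unblinding at the time of the primary analysis will be restricted to an independent unblinded statistician", with a programmer added if required. Whoever does this work may hold no other role in the study.
- **SAP 4.4, second paragraph**: "only pre-identified sponsor and unblinded CRO team members as specified in the study Data Blinding Plan will become unblinded to review treatment level results". The same sentence continues to individual listings: these people "will become unblinded to review treatment level results and individual listings".
- **SAP 4.4, first paragraph**: participants, assessing staff and Sponsor personnel "will be blinded to vaccination assignment until the EoS for Part A". It refers to protocol 5.3.8 for further detail.
- **SAP 6.7**, matching protocol 8.6.1: "all personnel involved in the conduct of the trial will remain blinded to individual treatment assignment until unblinding". That sentence opens with an exception for staff delegated an unblinded role, those giving the vaccine, and monitors. It then adds: "Investigators will be blinded until after the final database lock for final analysis".
- **SAP 7** reports no departures from the protocol's planned analyses. **SAP 1** gives the SAP precedence where its methods differ from the protocol's.

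**The concern.** The group and the time point are the same in protocol 5.3.8 and SAP 4.4, but the permission is reversed. The protocol stops at group-level knowledge, while the SAP goes on to individual listings. A sponsor team working from the SAP could open participant-level allocation at Day 29 and believe it was following the plan.

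This matters because sponsor judgement still shapes Part A data after Day 29:

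- Under protocol 7.4.2, either the investigator or the Sponsor can make an event serious. SAEs, MAAEs and AESIs to the end of study are a Part A primary endpoint (SAP 3.1.1).
- Protocol 7.5 and 10.2.11 assign the Sponsor medical monitor and safety physician to blinded safety monitoring. Study team members also decide when to request an ad hoc DSMB review. Nothing in the two documents excludes these roles from the pre-identified group.
- Per-protocol evaluability depends partly on medication and vaccine use during the study (protocol 5.5.3). SAP 6.2.6 has the major-deviation rules finalised before database lock without naming which lock.
- The immunogenicity sensitivity analyses are optional (SAP 6.4.2) and the subgroup analyses are a selection (SAP 6.5). Both leave choices that could be made with allocation known.

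**Working it through.** **1. Who may see what at the Part A Day 29 analysis**

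| Source | Pre-identified sponsor members | Independent statistician or programmer | Participants, assessors, investigators |
|---|---|---|---|
| Protocol 5.3.8 | Treatment group only | – | Blinded to end of Part A |
| Protocol 8.1 | No participant-level access | Participant level | – |
| SAP 4.4 | Treatment level and individual listings | Unblinded CRO members: same access | Participants and assessors blinded to end of Part A |
| SAP 6.7 and protocol 8.6.1 | Blinded to individual assignment unless delegated an unblinded role | A separate unblinded team runs the analysis | Investigators blinded to final lock |

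The conflict is confined to the sponsor column. No entry unblinds an observer.

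**2. How long the exposure can last**

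The plan states no figure for this, so there is none to reproduce. Inputs from the documents are the Day 29 visit, the last visit on Day 366, and the rule that the analysis follows completion of Day 29 in Part A and a data lock (SAP 6.7).

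Ceiling for one participant: (366 − 29)/(366 − 1) = 337/365 = 92.3%.

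The protocol's visit windows change this little. A Day 29 visit held on Day 22 gives (366 − 22)/365 = 94.2%; one held on Day 32 gives (366 − 32)/365 = 91.5%.

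**3. The cohort**

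The analysis waits for the Part A cohort, so earlier enrollees have used up more follow-up by then. Let E be the enrolment span and L the time to clean and lock, both in days. The documents give neither. I assume E = 30 to 120, L = 0 to 60, and uniform entry.

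- Last participant enrolled: (337 − L)/365
- First participant enrolled: (337 − E − L)/365
- Cohort mean: (337 − E/2 − L)/365

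| E | L | Last | Mean | First |
|---|---|---|---|---|
| 30 | 0 | 92.3% | 322/365 = 88.2% | 307/365 = 84.1% |
| 60 | 30 | 84.1% | 277/365 = 75.9% | 247/365 = 67.7% |
| 120 | 60 | 75.9% | 217/365 = 59.5% | 157/365 = 43.0% |

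With SAP 4.4 aligned to protocol 5.3.8 and 8.1, the sponsor members' share is zero until the end of Part A.

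**4. Which data are exposed**

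By the time of the analysis, the Day 29 immunogenicity and 7-day solicited reactions have been collected, and the data relevant to it through Day 29 are locked. The 28-day unsolicited AEs are essentially complete, apart from late entries and cleaning. Still open are SAEs, MAAEs and AESIs to Day 366, infection and COVID-19 cases, the Day 91, 181 and 366 immunogenicity, and later deviation decisions.

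**The case against.** The strongest reply is that the people who generate the data remain blinded. Protocol 5.3.8 states: "Part A of this study is an observer-blind study". Participants and assessing staff stay blinded to the end of Part A, and investigators to final lock. Investigators grade unsolicited events and judge causality (protocol 7.4.8 and 7.4.9), and solicited reactions are graded automatically from diary entries (protocol 7.4.3). This stands in full. A reader might infer from SAP 4.4 that the observer blind is broken, but the documents do not support that.

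Three further points have force:

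- **SAP 6.7 carves out delegated unblinded staff, and SAP 4.4 cross-refers to it.** If the pre-identified members are such staff, the two SAP sections can be read together. A contradiction inside the SAP is therefore not established. The carve-out does not settle the conflict with protocol 5.3.8, which addresses pre-identified Sponsor members by name of group and denies them individual knowledge.
- **The precedence clause in SAP 1 concerns methods.** Access to allocation is arguably a conduct rule, and SAP 4.4 itself points back to protocol 5.3.8. A reader might conclude that the looser rule governs; the text leaves that open. It remains a weakness that staff could act on either reading.
- **The Data Blinding Plan was not available.** It may name very few people, exclude the safety monitors, or mask identifiers in the listings. That could reduce the practical risk, but it would not make the SAP sentence agree with the protocol.

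It might also be said that only the CRO members were meant to see listings. The sentence does not draw that line, so it would still need correcting.

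**Conclusion.** The point holds as a conflict between protocol and SAP over the sponsor-side blind. SAP 4.4 grants pre-identified sponsor members participant-level access that protocol 5.3.8 withholds and protocol 8.1 reserves for an independent statistician or programmer, and SAP 7 does not declare it. The text mismatch is certain. The extent of any bias is not, because it depends on who the Data Blinding Plan names and how the listings are masked.

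A reader might take 92% as the share of the trial conducted under sponsor knowledge of allocation. It is a ceiling, reached only by the last participant enrolled with no lock delay. Under the stated assumptions the cohort average is about 60% to 88%. These percentages measure elapsed time, not bias.

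No hypothesis is tested (protocol 8.2), so there is no type I error or power consequence. The concern is greatest if the sponsor medical monitor, the safety physician or those classifying deviations are in the unblinded group. The correction should be made because it costs almost nothing and protects part of a primary safety endpoint.

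**What to change.** In SAP 4.4:

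1. Limit pre-identified sponsor members to treatment-level results at the Part A primary analysis.
2. State that individual unblinded listings stay with the independent statistician and programmer of protocol 8.1, working as the separate unblinded team of protocol 8.6.1 and SAP 6.7, until the final Part A database lock.
3. State that sponsor staff who carry out blinded safety monitoring or deviation review are excluded from participant-level access, and align the Data Blinding Plan.

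If individual access for sponsor members is truly intended, amend protocol 5.3.8 and 8.1 instead, and declare the change in SAP 7.

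The first route costs a short rewording of SAP 4.4 and a matching entry in the Data Blinding Plan. No data or analysis is lost. The sponsor members concerned wait until the final Part A lock for individual listings. The second route costs a protocol amendment.
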